2.5.3 Handling of missing values/censoring/discontinuations

Part A

A combination of treatment policy and composite strategy will be used to handle the intercurrent events.

A treatment policy will be used to handle (1) post-treatment initiation of all antivirals (including convalescent serum, antiviral antibodies, and antiviral small molecules) and immunosuppressive medications; and, (2) post-treatment increase in dose of immunosuppressive medications, for the treatment or management of COVID-19, and a patient will be evaluated regardless of experiencing either of these intercurrent events.

A composite strategy will be used to handle (3) death from any cause and (4) COVID-19 related hospitalization. In the event a patient experiences death or COVID-19 related hospitalization, all values after the time of death/start of the COVID-19 related hospitalization for change from baseline in \log_{10} SARS-CoV-2 viral load will be set as the worst observed value based on observed values at each time point within each treatment arm independently.

All measurements in \log_{10} SARS-CoV-2 viral load missing for other reason than death or COVID-19 related hospitalization will be imputed using last observation carried forward (LOCF) approach.

Part B

A treatment policy will be used to handle (1) post-treatment initiation of all antivirals (including convalescent serum, antiviral antibodies, and antiviral small molecules) and immunosuppressive medications; and, (2) post-treatment increase in dose of immunosuppressive medications, for the treatment or management of COVID-19, and a patient will be evaluated regardless of experiencing either of these intercurrent events.

Patients who prematurely discontinue the study and whose outcomes after discontinuation are not ascertainable will have follow up censored at the date of last known status.

2.5.4 Supplementary analyses

Part A

The following supplemental analysis will be performed:

- excluding patients who experienced a negative PCR COVID-19 test following a positive swab; and,
- imputing values below the LLOQ with the LLOQ value; and
- using the approach for the handling of the intercurrent events specified and jump-to-reference (J2R), a control-based pattern imputation method, for the handling of the remaining missing data.

Further details on supplementary analyses can be found in [Section 5.7.1](#).

Part B

Analysis will be specified a future SAP amendment as outlined in [Section 1](#).

2.5.5 Supportive analyses

For all analyses specified in this section, the estimand in [Section 2.5.1](#) and the missing data plan in [Section 2.5.3](#) for the primary analysis will be applied.

Part A

Subgroup analyses as described in [Section 2.2.1](#) will be performed as supportive analysis on primary variable. Subgroup analysis will be performed using ANCOVA but not the full MCP-mod procedure.

Change from baseline in \log_{10} SARS-CoV-2 viral load at visits (Day 3, Day 5 and Day 8) will be analyzed using a repeated measures ANCOVA (MMRM) including terms of treatment, baseline \log_{10} SARS-CoV-2 viral load, baseline risk of COVID-19 progression, presence of SARS-CoV-2 antibodies (Yes vs. No) and Geographical region (North America, Europe, Africa, Asia), visit, treatment*visit and baseline*visit interaction. Estimated treatment differences at visit and corresponding 95% CI will be tabulated and presented graphically.

MCP-mod procedure will be conducted for change from baseline at Day 8 in \log_{10} SARS-CoV-2 viral load as outlined in [Section 2.5.2](#). LSMeans and covariance estimates from the MMRM on change from baseline at Day 8 in \log_{10} SARS-CoV-2 viral load will be used to conduct the MCP-mod procedure. Similar outputs will be provided as in the primary analysis.

A descriptive summary will be provided for time-weighted change from baseline in \log_{10} SARS-CoV-2 viral load through Day 8. Additionally, for absolute values and change from baseline in \log_{10} SARS-CoV-2 viral load will be presented by visit.

Further details on supplementary analyses can be found in [Section 5.7.1](#).

Part B

Analysis will be specified a future SAP amendment as outlined in [Section 1](#).

2.6 Analysis of the key secondary objective

Not applicable. See [Section 2.7](#) for secondary objectives.

2.7 Analysis of secondary efficacy objectives

Part A

Secondary efficacy objectives for Part A are:

- To assess the effect of ensovibep, compared to placebo, in reducing the occurrence of hospitalizations (≥ 24 hours of acute care) and/or emergency room visits related to COVID-19 or death from any cause up to Day 29
- To assess the effect of ensovibep, compared to placebo, in reducing COVID-19 symptoms up to Day 29

All secondary efficacy endpoints will be analyzed using the FAS.

Part B

Analysis will be specified a future SAP amendment as outlined in [Section 1](#).

2.7.1 Secondary endpoints

2.7.1.1 Hospitalizations (\geq 24 hours of acute care) and/or emergency room visits related to COVID-19 or death from any cause up to Day 29

This secondary variable is defined as the event of experiencing

- Hospitalizations (\geq 24 hours of acute care) related to COVID-19; OR,
- Emergency room visits related to COVID-19; OR,
- Death from any cause.

If a patient experiences more than one of the events, the first event to occur will be counted towards the clinical efficacy endpoint and the date at which the first event occurred will be used as time date at which the clinical efficacy endpoint was achieved.

2.7.1.2 COVID-19 symptoms

Acute COVID-19 symptoms will be collected using a COVID-19 symptoms collection tool containing a 14-symptom questionnaire: feeling hot or feverish, chills or shivering, cough, sore throat, low energy or tiredness, headache, muscle or body aches, shortness of breath, nausea, vomiting, diarrhea, stuffy or runny nose, impaired sense of smell, and impaired sense of taste. The 14-symptoms will collectively be referred to as the FDA COVID-19 questionnaire ([FDA 2020a](#)).

At baseline, patients will have two or more COVID-19 symptoms as per inclusion criteria.

The endpoint to assess the reduction of COVID-19 symptoms up to Day 29 is time to sustained clinical recovery.

Sustained clinical recovery is defined as (a) all symptoms from the modified FDA COVID-19 symptom list scored as moderate or severe at baseline are subsequently scored as mild or absent, AND (b) all symptoms from the modified FDA COVID-19 symptom list scored as mild or absent at baseline are subsequently scored as absent, with no subsequent worsening, up to Day 29.

2.7.2 Statistical hypothesis, model, and method of analysis

2.7.2.1 Hospitalizations (\geq 24 hours of acute care) and/or emergency room visits related to COVID-19 or death from any cause up to Day 29

Proportion of patients experiencing hospitalizations (\geq 24 hours of acute care) and/or emergency room visits related to COVID 19 or death from any cause up to Day 29 will be presented along with relative risk to Placebo.

In addition, the number and percentage of patients with hospitalizations (≥ 24 hours of acute care) and/or emergency room visits related to COVID-19 or death from any cause up to day 29 will be summarized overall and separately for hospitalizations (≥ 24 hours of acute care), emergency room visits related to COVID-19 and death from any cause.

2.7.2.2 COVID-19 symptoms

The cumulative proportion of achieving sustained clinical recovery up to Day 29 will be estimated for each treatment group using Kaplan-Meier methods to take account of losses to follow-up.

The treatment differences in the estimated log cumulative proportion will be calculated and the variance for this difference will be obtained using Greenwood's formula. Two-sided 95% confidence intervals and associated p-value for the test of no difference between groups will then be obtained.

Number and percentage of patients with and without event will be tabulated along with the time at risk, event rates and corresponding 95%CI. Additionally, a Kaplan-Meier plot will be presented.

Time to sustained clinical recovery will be presented graphically with a Kaplan-Meier plot. A Cox proportional hazards model will be used, stratified by baseline risk of progression to severe COVID-19 and/or hospitalization ("high risk" vs. "not at high risk"). The model will include treatment, presence of SARS-CoV-2 antibodies (Yes vs. No), Geographical region (North America, Europe, Africa, Asia). Time of onset of COVID-19 symptoms (days relative to Day 1) will also be evaluated as a predictor in the model.

As a descriptive summary, shift tables presenting shifts from baseline to post-baseline will be provided for each question by selected visits (Day 3, Day 8, Day 15, and Day 29) and treatment group. Question on return to usual health and return to usual activities will be summarized for post-baseline visits only. Further a descriptive summary of the COVID-19 symptom score will be provided by scheduled timepoint. The symptom score ranges from 0 to 24 and includes eight domains (cough, breathlessness, feeling hot, fatigue, body pain, sore throat, chills and headache), each is graded on a scale of 0 (no symptoms) to 3 (severe symptoms).

Prior to database lock for primary analyses it was detected that due to non-compliance at sites some patients did not complete the COVID-19 symptom questionnaire prior to start of infusion. These patients do not have valid baseline data for COVID-19 symptom questionnaire. Therefore the following supportive analysis will be performed:

- 1) Time to sustained recovery analyses will be repeated using extended definition of sustained recovery: Sustained recovery is defined as (a) all symptoms from the modified FDA COVID-19 symptom list scored as moderate or severe at baseline are subsequently scored as mild or absent, AND (b) all symptoms from the modified FDA COVID-19 symptom list scored as mild or absent at baseline are subsequently scored as absent, with no subsequent worsening up to Day 29. For patients with missing baseline COVID-19 symptom questionnaire sustained recovery is defined as all symptoms from the modified FDA COVID-19 symptom list are scored as absent, with no subsequent worsening up to Day 29.

2) Time to event analyses will be repeated modifying baseline definition for COVID-19 symptom questionnaire. All values up to the end of infusion at Day 1 will be considered as baseline. Since the COVID-19 symptom questionnaire has a recall period of last 24 hours, study medication is unlikely to have an impact on patients' assessment of their symptoms over the last 24 hours, before infusion is completed.

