##### **12.5.1.3 COVID-19 symptoms**

Acute COVID-19 symptoms will be collected up to Day 29 to evaluate the efficacy of ensovibep using a COVID-19 symptoms collection tool containing a 14 symptoms questionnaire, collectively referred to as the FDA COVID-19 questionnaire ([FDA 2020a](#)). This questionnaire will be an eCOA tool completed by the patient. Each of the symptoms is rated on a scale of 0 to 3: 0 – none, 1 – mild, 2 – moderate, 3 – severe.

Sustained clinical recovery is defined as (a) all symptoms from the modified FDA COVID-19 symptom list scored as moderate or severe at baseline are subsequently scored as mild or absent, AND (b) all symptoms from the modified FDA COVID-19 symptom list scored as mild or absent at baseline are subsequently scored as absent, with no subsequent worsening, up to Day 29.

The cumulative proportion of achieving sustained clinical recovery up to Day 29 will be estimated for each randomized group using Kaplan-Meier methods to take account of losses to follow-up. Patients who prematurely discontinue the study and whose outcomes after discontinuation are not ascertainable will have follow up censored at the date of last known status.

The difference between randomized groups in the estimated log cumulative proportion will be calculated and the variance for this difference will be obtained using Greenwood’s formula.

Two-sided 95% CIs and associated p-value for the test of no difference between groups will then be obtained.

Time to sustained clinical recovery will be presented graphically with a Kaplan-Meier plot. A Cox proportional hazards model will be used, stratified by baseline risk of progression to severe COVID-19 and/or hospitalization (“high risk” versus “not at high risk”).

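### The only p-value named for time to sustained recovery comes from the Day 29 cumulative proportion, while the planned stratified Cox model has no stated output or role

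*SAP*

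**What the plan says.** SAP 2.7.1.2 defines the variable as a time: "The endpoint to assess the reduction of COVID-19 symptoms up to Day 29 is time to sustained clinical recovery". SAP 2.7.2.2 then sets out the analysis in this order.

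- Estimation: "The cumulative proportion of achieving sustained clinical recovery up to Day 29 will be estimated for each treatment group using Kaplan-Meier methods".
- Comparison: "The treatment differences in the estimated log cumulative proportion will be calculated", with a Greenwood variance.
- Inference: "Two-sided 95% confidence intervals and associated p-value for the test of no difference between groups will then be obtained".
- Description: counts with and without the event, time at risk, event rates with 95% CIs, and a Kaplan-Meier plot.
- Model: "A Cox proportional hazards model will be used, stratified by baseline risk of progression to severe COVID-19 and/or hospitalization". Treatment, baseline antibody status and region are terms, and time since symptom onset is to be examined as a predictor.

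Protocol 12.5.1.3 has the same structure: "The cumulative proportion of achieving sustained clinical recovery up to Day 29 will be estimated for each randomized group using Kaplan-Meier methods", followed by the log difference, its interval and p-value, a plot and a stratified Cox model. Neither section mentions a log-rank test. Neither says what will be reported from the Cox model or which of the two analyses leads.

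The Part B primary endpoint is treated differently. Protocol 12.4.2 and SAP 2.5.2 state there that hazard ratios and their 95% CIs will be computed from the stratified Cox model.

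**The concern.** The endpoint is a time, but the one comparison with a named test looks at a single point on the curve. Two patients who recover on Day 6 and Day 28 count the same. If a dose speeds recovery but the proportions recovered by Day 29 end up close, the named test has little to detect.

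The Cox model could answer the question of speed, but its place is open. Two analyses that can disagree are planned, and only one has a stated p-value. If they do disagree, the plan does not say which is the trial's result for this endpoint, and the choice would be made with the data in view. The endpoint is secondary in Part A and again in Part B, and the protocol text applies to both.

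**Working it through.** **Stated figure.** No power or effect size is given for this endpoint (SAP 3.3 says not applicable). The nearest stated figure is the Part A primary power, which fixes 100 patients per arm. Optimal contrasts for the five candidate shapes at doses 0, 75, 225 and 600 mg, one-sided 10%, critical value 1.688, effect 0.36 reached at 600 mg and the minimum over shapes give 90.1%, 85.4% and 80.4% at SD 1.0, 1.1 and 1.2. The plan states 90.03%, 85.25% and 80.25%, so the stated power reproduces.

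**Inputs.**
- From the documents: 100 per arm (SAP 3.1); two-sided 5% (Protocol 12); symptoms recorded daily to Day 15 and then weekly (Protocol Table 8-1, footnote 5).
- Assumed, because the documents give nothing: placebo recovery by Day 29 (F0) from 30% to 95%; recovery hazard ratio 1.3 or 1.5; proportional hazards.

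**Formulas.** Recovery in the active arm is F1 = 1 − (1 − F0)^HR.
- Day 29 test: z = ln(F1/F0) / √[(1 − F0)/(nF0) + (1 − F1)/(nF1)]. This is what the Greenwood variance reduces to without early censoring.
- Log-rank or Cox (Schoenfeld): z = ln(HR) × √(D/4), with D = n(F0 + F1) events.
- Power = Φ(z − 1.96).

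**Worked case, F0 = 0.90, HR 1.5.** F1 = 1 − 0.10^1.5 = 0.968.
- Day 29: ln(0.968/0.90) = 0.0732; SE = √(0.00111 + 0.00033) = 0.0379; z = 1.93; power 48.9%.
- Whole curve: D = 186.8; z = 0.405 × √46.7 = 2.77; power 79.1%.

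**Range, 100 per arm (power in %, Day 29 test vs log-rank/Cox).**

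| Placebo recovered by Day 29 | HR 1.5 | Loss, points | HR 1.3 | Loss, points |
|---|---|---|---|---|
| 30% | 38.5 vs 40.3 | 2 | 18.4 vs 18.8 | <1 |
| 50% | 54.2 vs 58.3 | 4 | 26.3 vs 27.8 | 2 |
| 60% | 58.9 vs 65.3 | 6 | 29.3 vs 32.0 | 3 |
| 70% | 61.1 vs 71.0 | 10 | 31.1 vs 36.0 | 5 |
| 80% | 59.2 vs 75.5 | 16 | 30.9 vs 39.7 | 9 |
| 90% | 48.9 vs 79.1 | 30 | 26.5 vs 43.0 | 17 |
| 95% | 35.3 vs 80.6 | 45 | 20.4 vs 44.5 | 24 |

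**Simulation check.** 4,000 runs with the protocol's assessment days, an assumed 5% loss to follow-up and HR 1.5 gave 53.5% vs 57.6% at 50% recovery, 59.9% vs 69.6% at 70%, and 46.7% vs 76.2% at 90%. These agree with the formulas.

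**Only speed differs.** Both arms were set to the same Day 29 proportion, with the recovery rate among those who recover 1.5 times higher on the active arm. The Day 29 test rejected in about 5% of runs, which is its alpha. The log-rank test rejected in 6%, 10% and 28% at 50%, 70% and 90% recovery.

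**In days.** With exponential times and 100 per arm, assumed medians of 10 vs 7 days give 45.5% vs 67.0%, and 8 vs 6 days give 28.2% vs 50.6%. With 858 per arm, about the Part B size, 8 vs 7 days gives 51.5% vs 76.1%. Placebo medians of 10 and 8 days imply about 87% and 92% recovered by Day 29, so all three cases sit at the unfavourable end of the table.

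**The case against.** The strongest reply is that timing is not discarded. A Cox model with a treatment term yields a hazard ratio, interval and p-value, and the general conventions (two-sided 5% p-values, 95% intervals) already fix their format. Neither document calls the Day 29 comparison the leading test. That is fair, and it narrows the point to an unstated output and an unstated order of precedence. It does not remove the point. Where the authors wanted the Cox result reported, for the Part B primary endpoint, they said so.

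The second reply is that a large power loss has not been shown. That also stands. A reader might infer that the curves have met by Day 29, because Protocol 1.1 says most patients get better in two to three weeks. That is general background and implies only more than half. The endpoint is stricter: symptoms that were mild at baseline must disappear, with no later worsening. No rate for that definition is given.

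A reader might also expect the gap between the tests to widen if the curves converge by Day 29. The simulation shows the opposite. With equal Day 29 proportions the gaps were about 1, 5 and 24 points at 50%, 70% and 90% recovery, against about 4, 10 and 30 under proportional hazards, because the log-rank test loses power too.

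Finally, the consequences are limited. There is no key secondary objective, no secondary estimand and no power claim for this endpoint, and SAP 2.7 defers the Part B secondary analyses to an amendment.

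**Conclusion.** The point holds as a gap in specification with a conditional cost. The only named p-value for a time-to-event endpoint tests a proportion at one time point. The planned analysis that uses timing has no stated output or precedence.

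Under proportional hazards the Day 29 test was the weaker of the two in every case computed. At 100 per arm and HR 1.5 the loss is 4 points or less up to 50% placebo recovery, about 6 to 10 points at 60% to 70%, and large only from about 80%. These figures rest on assumed recovery rates and hazard ratios. A moderate to large loss is plausible, but the documents do not establish it.

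Two stronger readings should be set aside. A reader might infer that the plan ignores timing altogether; the Cox model rules that out. A reader might also infer that this p-value drives the choice of the Part B dose. Protocol 12.4.2 and SAP 2.5.2 cite the clinical event rate, the symptom score and safety. They do not name time to sustained recovery, and SAP 2.7.2.2 summarises the 0 to 24 symptom score separately and descriptively.

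This should be fixed, but it does not threaten the primary analysis of either part.

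**What to change.** In SAP 2.7.2.2, state that the main treatment effect for time to sustained recovery is the hazard ratio for each dose against placebo, with 95% CI and p-value, from the planned Cox model stratified by risk. A log-rank test stratified by risk could supply the p-value instead. Report the Day 29 Kaplan-Meier proportions and their difference, with 95% CI, as supportive. Say that the two supportive repeats in that section, for patients without a valid baseline questionnaire, follow the same order. Align Protocol 12.5.1.3, and carry the rule into the SAP amendment planned before the first Part B patient.

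The cost is small. The model is already planned, and no extra data or patients are needed. The SAP change is a sentence or two, and for Part A it counts as prespecified only if made before unblinding for the primary analysis. The protocol change needs a written amendment with the approvals in Protocol 14.1. One statistical cost remains: the hazard ratio relies on proportional hazards for its interpretation, which is a reason to keep the Day 29 proportions and the Kaplan-Meier plot beside it.

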2.7.3 Handling of missing values/censoring/discontinuations

2.7.3.1 Hospitalizations (\geq 24 hours of acute care) and/or emergency room visits related to COVID-19 or death from any cause up to Day 29

Missing data will not be imputed.

2.7.3.2 COVID-19 symptoms

Missing data due to premature discontinuations prior to Day 29 are covered with the censoring approach.

Patients being too ill to complete the questionnaire will be considered as not achieving sustained recovery and will be censored at the earlier date or (last contact date, visit date of Day 29).

Patients who complete the questionnaire due to other reasons than 'being too ill to complete the questionnaire', do not achieve sustained recovery up to Day 29 and discontinue prior to Day 29 visit will be censored at the last date questionnaire was completed.

For any missing questionnaires between non-missing assessments, if reason for this is that patient is too ill to complete the questionnaire, the respective day will be considered as not achieving recovery.

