2.1.1.8 Last contact date

Last contact date is defined as the date the patients completes the study or discontinues prematurely. If a patient discontinues the study due to "lost to follow up" the latest date out of assessment dates and event/medication start and end dates will be used as last contact date.

For patients ongoing at time of primary analyses, the cut-off date will be used as last contact date.

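### In time to sustained recovery, patients too ill to answer who leave before Day 29 are censored on leaving, and deaths have no rule of their own, so the Kaplan-Meier recovery proportion is biased upward

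*SAP*

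**What the plan says.** Time to sustained clinical recovery up to Day 29 is a secondary efficacy endpoint in both Parts (SAP 1.2). Three pieces of text set the censoring.

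- **SAP 2.7.3.2, patients too ill to answer.** The classification is clear: "Patients being too ill to complete the questionnaire will be considered as not achieving sustained recovery". The censoring date follows in the same sentence: they "will be censored at the earlier date or (last contact date, visit date of Day 29". The word after *date* is evidently a slip for *of*, giving the earlier of the two dates.
- **SAP 2.1.1.8.** "Last contact date is defined as the date the patients completes the study or discontinues prematurely".
- **SAP 2.7.3.2, other early exits.** The opening line is general: "Missing data due to premature discontinuations prior to Day 29 are covered with the censoring approach". Patients with other reasons who have not recovered and who "discontinue prior to Day 29 visit will be censored at the last date questionnaire was completed".

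Protocol 12.5.1.3 covers the same endpoint more briefly: patients who discontinue early and "whose outcomes after discontinuation are not ascertainable will have follow up censored at the date of last known status".

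None of these passages mentions death. For the estimator, SAP 2.7.2.2 states: "The cumulative proportion of achieving sustained clinical recovery up to Day 29 will be estimated for each treatment group using Kaplan-Meier methods". The between-arm test uses the difference in log cumulative proportions with a Greenwood variance. A Cox model stratified by baseline risk is also fitted. The two supportive analyses there deal only with missing baseline questionnaires.

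**The concern.** Kaplan-Meier and Cox treat a censored patient as someone whose later chance of recovery matches that of patients still under observation. A patient who leaves because of illness is unlikely to fit that, and a patient who has died cannot. Censoring such patients on the day they leave lets the rest of the arm stand in for them, although the SAP's own sentence calls the too-ill patients non-recoveries. The stated intent and the censoring date therefore disagree.

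The error grows with the share of such patients in an arm. If they are commoner on placebo, part of a real benefit disappears; if they are commoner on ensovibep, part of a real harm does.

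The treatment of death also sits oddly with the rest of the plan. For the Part A primary endpoint, death and COVID-19 related hospitalization are unfavourable outcomes under a composite strategy (SAP 2.5.1 and 2.5.3). For recovery, a death would be handled as uninformative missing data.

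**Working it through.** The documents give no recovery rate, power or sample size for this endpoint (SAP 3.3), so there is no planned figure to reproduce. The check has two steps: follow the rule, then size its effect under stated assumptions.

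**Step 1: follow the rule.** Take two patients too ill to answer, neither recovered.

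- One stays in the study. Last contact is after the Day 29 visit, so the earlier date is Day 29. The patient stays at risk throughout and counts as a non-recovery. This is correct.
- The other leaves on Day 8. Last contact is Day 8, which is earlier than Day 29. The patient leaves the risk set on Day 8.

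A patient who dies on Day 8 has no rule of their own. Under the SAP's opening line the censoring date would be last contact or the last completed questionnaire, again around Day 8.

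**Step 2: size of the bias.** Let *p* be the share of an arm that never recovers and is censored at day *c*. Among the others, let *a* be the proportion not yet recovered at *c*, and *q* the chance that someone unrecovered at *c* is still unrecovered at Day 29.

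- Kaplan-Meier recovered = 1 − [(1 − p)a + p]q
- True proportion recovered = (1 − p)(1 − aq)
- Overstatement = difference = p(1 − q)

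So Kaplan-Meier credits the affected share with the later recovery of the others.

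Assumptions, none from the documents: exponential recovery with median 10 days and exit at Day 10. Then a = 0.5 and q = 2^(−19/10) = 0.268.

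| Affected | Kaplan-Meier, 1 − (0.5 + 0.5p) × 0.268 | True, (1 − p) × 0.866 | Overstatement, p × 0.732 |
|---|---|---|---|
| 1% | 86.5% | 85.7% | 0.73 points |
| 2% | 86.3% | 84.9% | 1.46 points |
| 5% | 85.9% | 82.3% | 3.66 points |

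(Subtracting the rounded percentages gives 0.8, 1.4 and 3.6.)

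**Range.** A separate daily calculation used 100 patients per arm (the Part A planning size), 1 to 7 affected, exit at Day 5, 10 or 15, and 60% or 80% of the others recovering by Day 29.

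- Smallest overstatement: 59.8% censored against 59.4% retained, 0.4 points (1 affected, exit Day 15, 60% recovery).
- Largest: 79.6% against 74.4%, 5.2 points (7 affected, exit Day 5, 80% recovery).

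**Two arms.** Suppose recovery among the others is equal, and 6 placebo and 1 active patient per 100 leave at Day 7. The true difference is 5 × 0.60 = 3.0 or 5 × 0.80 = 4.0 points. With early censoring, Kaplan-Meier shows about 0.5 points in both cases. Most of the difference is lost.

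**The case against.** The strongest points on the other side concern scope and size.

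- **Deaths.** A reader might infer that the SAP directs deaths to be censored. It does not say so; that is an inference from the general discontinuation rule. Protocol 12.5.1.3 limits its censoring to outcomes that cannot be ascertained, and non-recovery after death arguably can be. For deaths, the supportable statement is that no rule is given and that the SAP's default is censoring. A rule is still needed.
- **Dose selection.** A reader might infer that the Part A dose ranking is distorted. The documents do not support this. SAP 2.5.2 and Protocol 12.4.2 name the viral-load result, the rate of hospitalization, emergency visits or death, the symptom score, and safety. Time to recovery is not listed.
- **Part B.** A reader might infer that a wrong rule is already fixed for 1717 patients. The protocol's short rule applies generally, but SAP 1 and 2.7 leave the Part B analysis to a later amendment.
- **Size.** A 5% share is extreme. The planning rate for all hospitalizations, emergency visits and deaths together is 6.5% on placebo (SAP 3.1), and the SAP document history expects very few such events in Part A. Protocol 9.1.1 keeps patients who stop treatment in follow-up unless they withdraw consent. At 1% the bias is under one patient per 100. This stands.
- **Partial safeguard.** SAP 2.7.2.2 also tabulates numbers with and without the event, and deaths are reported elsewhere. The outcomes are therefore visible, but the Kaplan-Meier proportion, its interval and its p-value are not corrected.
- **Cox.** Censoring at death gives a cause-specific hazard ratio, which is a recognised quantity, and Protocol 2.2 sets no secondary estimand. This stands, so the charge of bias is limited to the Kaplan-Meier proportion.

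**Conclusion.** The point holds for the Kaplan-Meier proportion recovered by Day 29. For too-ill patients who leave early, it follows directly from SAP 2.7.3.2 and 2.1.1.8, and the censoring date defeats the classification in the same sentence. For deaths, the fault is a missing rule with an unsuitable default. Too-ill patients who remain in the study are handled correctly.

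The direction is certain if the affected patients do not recover: the proportion is overstated by p(1 − q). The size depends on assumed inputs: about 0.7, 1.5 and 3.7 points at 1%, 2% and 5% affected with a 10-day median and exit at Day 10, and 0.4 to 5.2 points across the wider range tried. In Part A the lower end is the more likely. No planned sensitivity analysis would show the effect. The matter is worth correcting because following the text gives a wrong estimate and the remedy is cheap, not because it threatens the primary result.

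**What to change.** In SAP 2.7.3.2, state that patients who die before Day 29, and patients too ill to complete the questionnaire who then leave the study, count as not recovered and are censored at Day 29, so that they stay in the risk set. Keep early censoring only for loss to follow-up unrelated to illness. Correct the slip in the too-ill sentence at the same time. Write the same rule into the Part B SAP amendment.

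The cost is one sentence and a small change to the censoring derivation. No new data are needed: Protocol 8.3.3 already has the too-ill reason recorded in the eCRF, and 8.3.2 has deaths recorded on the CRF. For Part A the change must be in place before the primary analysis, since SAP 1 says secondary efficacy analyses are not repeated at the final analysis.

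There is one small downside to state. With these patients kept at risk, the Cox model estimates a subdistribution-type hazard ratio instead of a cause-specific one. The SAP should say so.
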